5.5. Analysis of Secondary Outcomes

Secondary outcomes for analyses include change in self-reported hours worked per week, change in self-reported sexual risk behavior, change in chlamydia test results, change in gonorrhea test results, and reactive HIV test result. Details about these outcomes are described in Section 4.2.

Univariate analyses will be performed as described in Section 5.1. Multivariable analyses will adjust for sociodemographic characteristics, workshop attendance, baseline employment status, and study completeness. Analytical models will include linear regression or generalized linear models for continuous outcomes and logistic regression for binary and categorical outcomes.

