#### 4.1.4 Phase 2 Intervention Pre Test & Pilot-Test Inclusion Criteria

Must meet the following eight criteria:

1. Male or assigned male at birth (YTW)
2. Identifies as a man who has sex with men (YMSM) and/or gay bisexual man or transgender woman/transwoman
3. Identifies as African American/Black, Hispanic/Latino, and/or as a racial/ethnic minority or person of color
4. 16-24 years old
5. English-speaking (primary)
6. HIV negative or of unknown status
7. Currently unemployed but seeking employment or employed only part-time 35 hrs or less on avg/wk)
8. Able to attend a 4-session employment program

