1.1. Objectives and Research Hypotheses

The primary objective of Phase 2 is to pilot-test the intervention among up to 70 at-risk YMSM and YTW of color in order to evaluate feasibility and acceptability. Investigators hypothesize the intervention will increase job self-efficacy and readiness, as well as decrease HIV risk behaviors and STI and HIV infections.

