2.3. Sample Size Information

This study aims to enroll up to 70 participants with at least 50 of these participants completing the study (~70% retention rate). Given the exploratory nature of this study and limited access to this population, a power calculation was not performed. A repeated measures design was chosen to reduce the variability in the estimate of the treatment effect, at the expense of having a comparison group. In addition, practice or fatigue effects from repetition may affect certain outcomes (e.g. protean career attitudes scale and subscales). This trade-off was appropriate given the exploratory nature of a pilot study and the limited access to the study population.

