5.4. Analysis of Primary Outcomes

Primary outcomes for analyses include Information Systems Success Model score, workshop completion, change in Job-Seeking Self Efficacy Scale score, Protean Career Attitudes Scale score, change in Self-Directed Attitudes Scale score, and change in Values-Driven Attitudes Scale score. Details about these outcomes are described in Section 4.1.

Univariate analyses will be performed as described in Section 5.1. To the extent that data allows, multivariable analyses will adjust for sociodemographic characteristics, workshop attendance, baseline employment status, and study completeness. Analytical models will include linear regression or generalized linear models for continuous outcomes and logistic regression for binary and categorical outcomes.

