2.3. Sample Size Information

This study aims to enroll up to 40 participants. Given the exploratory nature of this study and limited access to this population, a power calculation was not performed. A repeated measures design was chosen to reduce the variability in the estimate of the treatment effect, at the expense of having a comparison group. In addition, practice or fatigue effects from repetition may affect certain outcomes (e.g. protean career attitudes scale and subscales). This trade-off was appropriate given the exploratory nature of a pilot study and the limited access to the study population.

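### Both SAPs require adjusted logistic regression for the T3 HIV result with no data-sufficiency limit, although the events likely to be available rarely allow a finite estimate

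*SAP*

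**What the plan says.** Section 5.5 lists five secondary outcomes in each SAP: change in hours worked, change in sexual risk behavior, change in chlamydia results, change in gonorrhea results, and the reactive HIV result. It then states "Multivariable analyses will adjust for sociodemographic characteristics, workshop attendance, baseline employment status, and study completeness", and specifies "logistic regression for binary and categorical outcomes". The wording is the same in Phase 2 and Phase 3.

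Section 5.4, for primary outcomes, opens the same instruction with a limit: "To the extent that data allows, multivariable analyses will adjust for sociodemographic characteristics". Section 5.5 has no such limit, and it names no penalised, exact or descriptive alternative.

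Section 4.2.5 defines the HIV outcome as the T3 result alone. The tests in 5.1 are paired tests of change, so none applies to it. Apart from the frequencies promised in 5.1, the adjusted logistic model is the only analysis specified for HIV.

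On sample size, section 2.3 of the Phase 2 SAP aims for up to 70 enrolled and at least 50 completing. The Phase 3 SAP says "This study aims to enroll up to 40 participants" and gives no retention figure. Both say "a power calculation was not performed".

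Section 1.1 of both SAPs hypothesises that the intervention will raise job self-efficacy and readiness, "as well as decrease HIV risk behaviors and STI and HIV infections". Phase 2 admits people who are "HIV negative or of unknown status" (Protocol 4.1.4). Phase 3 admits known positives but does not test them (Protocol 3.4). In both phases, anyone with known positive status at follow-up is not tested (Protocol 6.5).

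**The concern.** The limit is present where the outcomes are mostly continuous and absent where events are rarest. A logistic model needs events spread across the levels of its covariates. If every event falls at one level of a binary covariate, the likelihood keeps rising as that coefficient grows, and no finite maximum exists. Software may then stop with an error, or print a very large odds ratio that reflects only its stopping rule. An analyst following 5.5 literally would have to report such a result for HIV.

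The hypothesis in 1.1 adds a smaller problem. It names a decrease in HIV infections, but the outcome is a single-arm count at T3 with no comparator.

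**Working it through.** **1. The plan's own figure.** 50/70 = 71.4%, which agrees with the stated retention of about 70%. For Phase 3 I assume either full retention (40) or the same 70% (0.70 × 40 = 28). SAP 3.1 uses T3 completers for these outcomes. Specimens are optional (Protocol 8.3), so the number tested may be lower.

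**2. Time at risk.** Phase 2: 8 months = 0.667 years. The longest window from T1 is 12 weeks + 8 months + 4 weeks, about 0.97 years. Phase 3: 3 months = 0.25 years. The longest window is 4 weeks + 3 months + 2 weeks, about 0.37 years.

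**3. Expected HIV events.** The documents give no incidence. I assume λ = 1 to 8 per 100 person-years. Expected events = n × (1 − exp(−λt)); P(0 events) = exp(−nλt).

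| Setting | Expected events, λ = 1 to 8 | P(0 events) |
|---|---|---|
| Phase 2, n=50, 8 months | 0.33 to 2.6 | 72% to 7% |
| Phase 2, n=50, longest window | 0.5 to 3.75 | 61% to 2% |
| Phase 3, n=40, 3 months | 0.10 to 0.79 | 90% to 45% |
| Phase 3, n=40, longest window | 0.15 to 1.15 | 86% to 31% |
| Phase 3, n=28, 3 months | 0.07 to 0.55 | 93% to 57% |

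If all 70 Phase 2 participants completed, the longest-window range would be 0.68 to 5.25.

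**4. When the model has no finite estimate.** With 0 events nothing can be estimated. With 1 event, that event necessarily sits at one level of every binary covariate, so no finite maximum exists. With k events and one binary covariate of prevalence p unrelated to outcome, the chance that all events share a level is p^k + (1−p)^k. Protocol Appendix III plans 18 of 70 Hispanic or Latino:

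- k=2: (18² + 52²)/70² = 3,028/4,900 = 62%
- k=3: (18³ + 52³)/70³ = 146,440/343,000 = 43%

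That is for one covariate. The SAP does not list its sociodemographic variables, so the full model needs assumed sets. Five terms: age, ethnicity, gender identity, workshops attended, baseline employment. Six: the same kind of set plus education. Nine: adds education, housing and a completeness flag to the five. Outcomes were simulated independently of the covariates, and each data set (400 to 600 per cell) was checked for complete or quasi-complete separation by linear programming. Share with no finite estimate at n=50:

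| Events | 5 terms | 6 terms | 9 terms |
|---|---|---|---|
| 1 | 100% | 100% | 100% |
| 2 | 95% | 97% | 100% |
| 3 | 75% | 83% | 99% |
| 5 | 44% | 48% | 86% |
| 8 | 15% | not run | 51% |

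At n=28 with 5 terms the shares were 96% (2 events) and 82% (3 events).

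Averaging over the number of events at 2 to 8 per 100 person-years with 5 terms, the Phase 2 HIV model failed in 98% to 78% of data sets over 8 months, and in 97% to 65% over the longest window. The Phase 3 model failed in 98% to 100%.

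**5. Site-level STI results.** The documents give no positivity rate either. For an assumed share in the modelled category of 2, 5, 10 and 15%, non-finite fits at n=50 were 97, 82, 46 and 27% with 5 terms, and 100, 98, 82 and 59% with 9 terms. At n=28 with 5 terms they were 99, 98, 78 and 59%. These runs treat one category against the rest. The −1/0/+1 change coding in the SAP appendix was not simulated.

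**6. What a count gives.** For 0 of n, the upper limit of an exact two-sided 90% interval is 1 − 0.05^(1/n): 5.8% for 0/50, 7.2% for 0/40 and 10.1% for 0/28.

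**The case against.** These are secondary outcomes of an exploratory pilot with no power calculation, and no primary outcome is affected. Section 5.1 already promises frequencies at each time point, so counts will appear in any case. A competent analyst would usually notice a failed fit. The event range, the Phase 3 completers and the covariate lists are all assumptions. This fairly limits the severity and means that the percentages are indicative. It does not remove the problem, because the 0- and 1-event cases need no simulation and the SAP gives no instruction for when the model fails. The alpha 0.2 screen in Protocol 10.3.1.2 does not clearly help, since it concerns mediators and effect modifiers.

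A reader might infer that every site-level STI model fails in the same way and should be dropped. The documents do not support that. With no rate stated, failure is usual only if a category is rare (about 5% or less at n=50 with 5 terms), the sample is as small as 28, or the covariate set is large. At 10–15% with a small model at n=50, most fits are finite, though unstable.

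A reader might also infer that no fall in HIV could ever appear in the data. That goes too far. Nobody's HIV status reverts, but the share reactive among those tested could drop from T1 to T3 because known positives are not retested. That drop would be an artefact. Nor does any passage plan to read few reactive tests as a decrease, and Protocol 2.4 hypothesises only lower HIV risk behavior.

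**Conclusion.** The point holds for HIV. As written, 5.5 makes an adjusted logistic model compulsory for an outcome with an assumed 0.3–3.8 events in Phase 2 (50 completers) and under about 1.2 in Phase 3 (28–40 completers). The model has no finite estimate with 0–1 events, and in roughly 75–97% of simulated data sets with 2–3 events (n=50, 5–6 covariates). Four or more events become likely only at the top of the assumed incidence range with the longest window, or if nearly all 70 complete.

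For the STI results the defect is the missing limit, not the existence of the models.

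The hypothesis wording is a minor point. A T3-only count in a single arm, with known positives not retested, cannot show a true decrease in infections. The SAP also does not say how participants reactive at T1 enter the T3 outcome. Protocol 3.4 makes skipping the follow-up test depend on documentation of a prior diagnosis, so some could be retested and counted although they are not new infections.

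**What to change.** In 5.5 of both SAPs:

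1. Take the reactive HIV result out of the multivariable sentence. Report the number reactive over the number tested at T3 with an exact 90% confidence interval, which matches the planned alpha of 0.1. State how participants reactive at T1 are handled, for example by reporting new reactive results among those non-reactive at T1.
2. Add the 5.4 limit for the remaining secondary outcomes. Where events are too few to model, report site-level STI positives over number tested with exact intervals. Fix the cut-off before the results are seen; the table by event count above can guide it.

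Minor: in 1.1 of both SAPs, replace the hypothesised decrease in HIV infections with a descriptive count of new reactive results. This also brings the SAP closer to Protocol 2.4.

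The cost is SAP wording. No data collection changes and fewer models are run. What is lost is an adjusted HIV odds ratio.

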5.6. Analysis of Safety Events

Safety Events will be recorded for participants as needed throughout the study. The number of participants experiencing each safety event will be summarized by severity grade, relationship

to study, and action taken. All safety events will be provided in the safety events data listing. Withdrawals due to safety events will also be reported.

REFERENCES

APPENDIX

1. PRIMARY OUTCOMES

1.1. INFORMATION SYSTEMS SUCCESS MODEL (ISSM) SCALE

The Information Systems Success Model (ISSM) scale has been adapted from Horvath et al. 2013 to assess intervention acceptability and satisfaction. The scale evaluates four sub-domains: information quality, system quality, perceived usefulness, and overall satisfaction. For each of the calculated scores, higher values indicate better participant-assessed quality.

1.1.1. ISSM Subscale 1: Information Quality (IQ) Score

Description: Information Quality is a 6-item sub-scale measured at time point T2 (post-intervention) to evaluate ease of comprehension, credibility, clarity, and accuracy of the information provided through the intervention using responses to items 7a through 7e and 8a in the Evaluation (EVL) Questionnaire. Responses are scored as 1/Strongly Disagree = 1 point, 2/Disagree = 2 points, 3/Neither Disagree nor Agree = 3 points, 4/Agree = 4 points, and 5/Strongly Agree = 5 points.

Variable: IQ_T2_1

Label: Information Quality Score at T2

Type: Numeric; Range = 1 to 5

Algorithm: IQ_T2_1 = MEAN (EVL7a, EVL7b, EVL7c, EVL7d, EVL7e, EVL8a)

If all responses are missing, then then IQ_T2_1=Missing. Otherwise, consider mean of non-missing responses.

1.1.2. ISSM Subscale 2: Handbook Quality (HQ) Score

Description: Handbook Quality is a 6-item sub-scale measured at time point T2 (post-intervention) to evaluate user friendliness and appeal of the workshop handbook provided through the intervention using responses to items 8b through 8e, 9a, and 9b in the EVL Questionnaire. Responses are scored as 1/Strongly Disagree = 1 point, 2/Disagree = 2 points, 3/Neither Disagree nor Agree = 3 points, 4/Agree = 4 points, and 5/Strongly Agree = 5 points.

Variable: HQ_T2_1

Label: Handbook Quality Score at T2

Type: Numeric; Range = 1 to 5

Algorithm: $HQ_T2_1 = \text{MEAN} (\text{EVL8b, EVL8c, EVL8d, EVL8e, EVL9a, EVL9b})$

If all responses are missing, then $HQ_T2_1 = \text{Missing}$. Otherwise, consider mean of non-missing responses.

1.1.3. ISSM Subscale 3: Perceived Usefulness (PU) Score

Description: Perceived Usefulness is a 6-item sub-scale measured at time point T2 (post-intervention) to evaluate the usefulness of the intervention to help the participant to achieve their career-related goals using responses to items 6c, 9c through 9e, 10a, and 10b in the EVL Questionnaire. Responses are scored as 1/Strongly Disagree = 1 point, 2/Disagree = 2 points, 3/Neither Disagree nor Agree = 3 points, 4/Agree = 4 points, and 5/Strongly Agree = 5 points.

Variable: PU_T2_1

Label: Perceived Usefulness Score at T2

Type: Numeric; Range = 1 to 5

Algorithm: $PU_T2_1 = \text{MEAN} (\text{EVL6c, EVL9c, EVL9d, EVL9e, EVL10a, EVL10b})$

If all responses are missing, then $PU_T2_1 = \text{Missing}$. Otherwise, consider mean of non-missing responses.

1.1.4. ISSM Subscale 4: Overall Score

Description: The Overall Score is a 3-item sub-scale measured at time point T2 (post-intervention) to evaluate the overall satisfaction with the workshops using responses to items 10c through 10e from the EVL Questionnaire. Responses are scored as 1/Strongly Disagree = 1 point, 2/Disagree = 2 points, 3/Neither Disagree nor Agree = 3 points, 4/Agree = 4 points, and 5/Strongly Agree = 5 points.

Variable: OVERALL_T2_1

Label: Overall Score at T2

Type: Numeric; Range = 1 to 5

Algorithm: $OVERALL_T2_1 = \text{MEAN} (\text{EVL10c, (6 - EVL10d), EVL10e})$

If all responses are missing, then $OVERALL_T2_1 = \text{Missing}$. Otherwise, consider mean of non-missing responses.

1.1.5. Information Systems Success Model (ISSM) Score

Description: The ISSM Score is obtained by adding the four subscale scores defined above: IQ Score, HQ Score, PU Score, and Overall Score.

Variable: ISSM_T2_1

Label: Information Systems Success Model Score at T2

Type: Numeric; Range = 1 to 5

Algorithm: ISSM_T2_1 = MEAN (IQ_T2_1, HQ_T2_1, PU_T2_1, OVERALL_T2_1).

If all responses are missing, then ISSM_T2_1=Missing. Otherwise, consider mean of non-missing responses.

1.2. WORKSHOP COMPLETION

Workshop completion will be used in the assessment of intervention feasibility. The primary outcome for workshop completion will be measured using a binary outcome of Complete vs. Not Complete (1.2.2), but the number of completed workshops (1.2.1) is also defined to assess potential dose response of the workshop intervention on other outcomes.

1.2.1. Number of Workshops Attended

Description: The participants' workshop attendance is recorded in items 3a, 3c, 4a, 4c, 5a, 5c, 6a, and 6c of the Workshop Tracking Information (WTI) form.

Variable: WSATTEND_T2_1

Label: Number of Workshops Attended at T2

Type: Numeric; Range = 0 to 4

Algorithm: WSATTEND_T2_1 = SUM (WTI3a, WTI3c, WTI4a, WTI4c, WTI5a, WTI5c, WTI6a, WTI6c)

If all responses are missing, then WSATTEND_T2_1=Missing. Otherwise, sum non-missing responses. Note: WTI#c can only have a response if WTI#a=0.

1.2.2. Workshop Completion

Description: Workshop completion is defined as having attended at least two of the four workshop sessions (50% completion).

Variable: WSCOMP_T2_1

Label: Workshop Completion at T2

Type: Numeric; Format: 0=Not Complete, 1=Complete, .=Missing

Algorithm: If WSATTEND_T2_1 >= 2 then WSCOMP_T2_1 = 1
Else if WSATTEND_T2_1 in (0, 1) then WSCOMP_T2_1=0
Else WSCOMP_T2_1 = .

1.3. JOB SEEKING SELF-EFFICACY SCALE SCORE

Job seeking self-efficacy is defined as one's perceived ability and confidence to perform job search and application activities. Higher values indicate higher self-efficacy. This scale is measured at Baseline (T1) and the Month 8 Follow-up (T3).

1.3.1. Job Seeking Self-Efficacy Score at Baseline (T1)

Description: Job Seeking Self-Efficacy score at time point T1 (Baseline) is based on 12 items (52a through 52f and 53a through 53f) from the BSL Questionnaire. Responses are scored on the scale 1/Not at all confident = 1 point to 10/Very Confident = 10 points.

Variable: JOBSEEK_T1_1

Label: Job-Seeking Self Efficacy Score at T1

Type: Numeric; Range = 1 to 10

Algorithm: JOBSEEK_T1_1 = MEAN(BSL52a, BSL52b, BSL52c, BSL52d, BSL52e, BSL52f, BSL53a, BSL53b, BSL53c, BSL53d, BSL53e, BSL53f)

If all responses are missing, then JOBSEEK_T1_1=Missing. Otherwise, calculate the mean of the non-missing responses.

1.3.2. Job Seeking Self-Efficacy Score at Post-Intervention (T2)

Description: Job Seeking Self-Efficacy score at time point T2 (Post-Intervention) is based on 12 items (13a through 13f and 14a through 14f) from the EVL Questionnaire. Responses are scored on the scale 1/Not at all confident = 1 point to 10/Very Confident = 10 points.

Variable: JOBSEEK_T2_1

Label: Job-Seeking Self Efficacy Score at T2

Type: Numeric; Range = 1 to 10

Algorithm: $\text{JOBSEEK_T2_1} = \text{MEAN} (\text{EVL13a, EVL13b, EVL13c, EVL13d, EVL13e, EVL13f, EVL14a, EVL14b, EVL14c, EVL14d, EVL14e, EVL14f})$

If all responses are missing, then $\text{JOBSEEK_T2_1}=\text{Missing}$. Otherwise, calculate the mean of the non-missing responses.

1.3.3. Job Seeking Self-Efficacy Score at Month 8 Follow-Up (T3)

Description: Job Seeking Self-Efficacy score at time point T3 (Month 8 follow-up) is based on 12 items (52a through 52f and 53a through 53f) from the EXQ Questionnaire. Responses are scored on the scale 1/Not at all confident = 1 point to 10/Very Confident = 10 points.

Variable: JOBSEEK_T3_1

Label: Job-Seeking Self Efficacy Score at T3

Type: Numeric; Range = 1 to 10

Algorithm: $\text{JOBSEEK_T3_1} = \text{MEAN} (\text{EXQ52a, EXQ52b, EXQ52c, EXQ52d, EXQ52e, EXQ52f, EXQ53a, EXQ53b, EXQ53c, EXQ53d, EXQ53e, EXQ53f})$

If all responses are missing, then $\text{JOBSEEK_T3_1}=\text{Missing}$. Otherwise, calculate the mean of non-missing responses.

1.3.4. Change in Job Seeking Self-Efficacy Score from Baseline to Month 8 Follow-Up (T1T3)

Description: Difference between Job Seeking Self-Efficacy score at the Month 8 follow-up (T3) and the score at Baseline (T1). If the Job Seeking Self-Efficacy score is missing at T3, then the score from T2 is used to compute the change in score from T1.

Variable: JOBSEEK_T1T3_1

Label: Change in Job-Seeking Self Efficacy Score from T1 to T3 (T3-T1)

Type: Numeric; Range = -9 to 9

Algorithm: If $\text{JOBSEEK_T3_1} \neq \text{Missing}$, then $\text{JOBSEEK_T1T3_1} = \text{JOBSEEK_T3_1} - \text{JOBSEEK_T1_1}$
Else if $\text{JOBSEEK_T3_1} = \text{Missing}$, then $\text{JOBSEEK_T1T3_1} = \text{JOBSEEK_T2_1} - \text{JOBSEEK_T1_1}$

If JOBSEEK_T1_1 is missing, then $\text{JOBSEEK_T1T3_1}=\text{Missing}$. If JOBSEEK_T2_1 and JOBSEEK_T3_1 are missing, then $\text{JOBSEEK_T1T3_1}=\text{Missing}$.

1.4. PROTEAN CAREER ATTITUDES SCALE (PCA) SCORE:

Protean career attitudes are defined as having self-direction in the pursuit of success in one's work. The scale (and the two sub scales) were measured at Baseline (T1) and the Month 8 follow-up (T3). Higher values indicate better attitudes.

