3.1. Intent-to-Treat Population

All participants who completed T3 will be included in intent-to-treat analyses involving variables measuring changes from T1 to T3 (see sections 4.1.3-4.1.4 and 4.2.1-4.2.5 below).

All participants who completed at least one workshop will be included in intent-to-treat analyses involving workshop evaluation and workshop completion variables (see sections 4.1.1,

¹ The original inclusion criteria included "Considered 'at-risk' for HIV based on 6-item risk assessment". The removal of this criterion was approved on August 16, 2018 as part of protocol v4.0 and eligibility was rerun retrospectively for those who completed the Screener Survey (SCR) prior to the inclusion criteria modification.

4.1.2 below). This population will form the basis for both the primary and secondary analyses of the efficacy and safety endpoints.

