3.2. Per Protocol Population

Youth who attend at least two of the four planned intervention workshops and complete T3 will comprise the per protocol population. This population will form the basis for both the primary and secondary supportive analyses of the efficacy and safety endpoints.

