4.1.3. Change in Job-Seeking Self-Efficacy Scale Score (T1 to T3)

Job seeking self-efficacy is defined as one's perceived ability and confidence to perform job search and application activities. The 12-item Job Seeking Self-Efficacy (JSS) scale by Barlow et al² uses response values on a 1 to 10 score, with 1 being "Not At All Confident" and 10 being "Very Confident". Responses are averaged to yield a total score, with higher scores indicating higher self-efficacy. Change in JSS will be calculated by subtracting the JSS score at baseline (T1) from the JSS score at the 8-month follow-up (T3) (range: -9 to +9; negative change indicates decreased self-efficacy, while positive change indicates increased self-efficacy).

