5.2. Missing Data

Missing responses to survey questions will be ignored and non-missing data will be used to compute the primary and secondary outcomes. If all components for an outcome are missing, then the outcome will be considered missing. For those outcomes with unique missing data rules, the handling of missing data for each individual outcome are described in the appendix. Missing data patterns will be explored prior to the analysis of the primary and secondary outcomes.

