1.4.1.3. Change in Self-Directed Attitudes Score from Baseline to Month 8 Follow-Up (T1T3)

Description: Difference between Self-Directed Attitudes score at time point T3 (Month 8 follow-up) and time point T1 (Baseline)

Variable: SDA_T1T3_1

Label: Change in Self-Directed Attitudes Score from T1 to T3 (T3-T1)

Type: Numeric; Range = -4 to 4

Algorithm: $SDA_T1T3_1 = SDA_T3_1 - SDA_T1_1$

If SDA score at either time point is missing, then SDA_T1T3_1=Missing.

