4.1.3. Change in Job-Seeking Self-Efficacy Scale Score (T1 to T3)

Job seeking self-efficacy is defined as one’s perceived ability and confidence to perform job search and application activities. The 12-item Job Seeking Self-Efficacy (JSS) scale by Barlow, Wright, & Cullen² uses response values on a 1 to 10 score, with 1 being “Not At All Confident”

and 10 being “Very Confident”. Responses are averaged to yield a total score, with higher scores indicating higher self-efficacy. Change in JSS will be calculated by subtracting the JSS score at baseline (T1) from the JSS score at the 3-month follow-up (T3) (range: -9 to +9; negative change indicates decreased self-efficacy, while positive change indicates increased self-efficacy).

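### The primary self-efficacy change labelled T3-T1 takes the T2 score when T3 is missing, and section 3.1 of each SAP does not settle whether people with T2 but no T3 are analysed

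*SAP*

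**What the plan says.** Section 4.1.3 of the Phase 2 SAP defines the outcome without a fallback: "Change in JSS will be calculated by subtracting the JSS score at baseline (T1) from the JSS score at the 8-month follow-up (T3"). The Phase 3 SAP does the same at its own time point: "Change in JSS will be calculated by subtracting the JSS score at baseline (T1) from the JSS score at the 3-month follow-up (T3").

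Appendix 1.3.4, in the same words in both SAPs, adds the fallback: "If the Job Seeking Self-Efficacy score is missing at T3, then the score from T2 is used to compute the change". The algorithm below it computes T2 minus T1 in that case. The variable is still called `JOBSEEK_T1T3_1`, and its label still reads "Change in Job-Seeking Self Efficacy Score from T1 to T3 (T3-T1").

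On missing data, section 5.2 defers to the appendix: "For those outcomes with unique missing data rules, the handling of missing data for each individual outcome are described in the appendix". On who is analysed, section 3.1 says: "All participants who completed T3 will be included in intent-to-treat analyses involving variables measuring changes from T1 to T3". It lists 4.1.3 among those outcomes. Section 3.2 sets the per-protocol group: "Youth who attend at least two of the four planned intervention workshops and complete T3 will comprise the per protocol population".

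Protocol 10.4 plans one analysis restricted to cases that have the primary endpoint. It keeps people who missed workshops if they attend T3, and it provides for multiple imputation when the loss is substantial. It does not mention using T2 in place of T3.

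**The concern.** T2 and T3 answer different questions. T2 shows how confident people feel as training ends, and T3 shows whether that confidence lasts to 8 or 3 months. Under the appendix rule, one variable can hold both, and an output table headed T3-T1 would not show how many values are of each kind.

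The analysis set is also open. Section 3.1 includes T3 completers but neither excludes others nor defines completing T3. The appendix gives a usable change score to someone with T2 and no T3. One analyst could drop that person under 3.1, and another could keep them under the appendix.

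This outcome is one of several primary outcomes in an exploratory pilot. What is at stake is the meaning of one reported result and whether it can be reproduced.

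**Working it through.** **1. The rule compared with the other change variables.** Each SAP appendix defines 12 T1-to-T3 change variables: self-efficacy, SDA, VDA, PCA, hours worked, sexual risk, three chlamydia and three gonorrhea. Eleven are set to missing when either time point is missing, for example "If SDA score at either time point is missing, then SDA_T1T3_1=Missing". Self-efficacy alone is filled.

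**2. Two readings of section 3.1.**
- *T3 completion is required.* The fallback then reaches only people who attended T3 but left all 12 items blank, and the effect is negligible.
- *T3 completion is not required.* Section 3 uses the word *only* for baseline enrolment but not for T3, and 5.2 points to the appendix. Anyone with T1 and T2 then enters the T3-T1 analysis. In that case the SAPs specify no analysis of all observed-T3 cases. The per-protocol set comes close but omits T3 attenders with 0 or 1 workshop.

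**3. How many values could be filled (second reading).** Phase 2 SAP 2.3 plans at least 50 of 70 completing: 50/70 = 71.4%, which agrees with the stated figure of about 70%. The ceiling at that retention is 70 − 50 = 20 values, or 20/70 = 28.6%. The real count should be lower, because a fill needs a T2 score and protocol 8.2 lists only the follow-up visit for people who attended no workshop. Phase 3 states no retention. If 24 to 36 of 40 attend T3 (assumed), the ceiling runs from 16 (40%) to 4 (10%).

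**4. Bias.** Take as target the mean T3 change in everyone with T2 or T3. Let n3 be the number with observed T3, m the number filled, g3c the completers' T3 change, and g3d and g2d the dropouts' T3 and T2 change.
- Target: (n3·g3c + m·g3d)/(n3 + m)
- Bias of the filled analysis: m(g2d − g3d)/(n3 + m)
- Bias of the completers analysis: m(g3c − g3d)/(n3 + m)

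The documents give none of the three changes, so all are assumed here, in scale points. With n3 = 50, the first row is 10(1.0 − 0)/60 = 0.17 and 20(1.0 − 0)/70 = 0.29.

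| g3c | g3d | g2d | Filled, m = 10 / 20 | Completers, m = 10 / 20 |
|---|---|---|---|---|
| 0 | 0 | 1.0 | +0.17 / +0.29 | 0 / 0 |
| 0.5 | 0.5 | 1.0 | +0.08 / +0.14 | 0 / 0 |
| 0.5 | 0.5 | 0.5 | 0 / 0 | 0 / 0 |
| 1.0 | 1.0 | 0.5 | −0.08 / −0.14 | 0 / 0 |
| 0.5 | 0 | 0.25 | +0.04 / +0.07 | +0.08 / +0.14 |
| 0.5 | 0 | 1.0 | +0.17 / +0.29 | +0.08 / +0.14 |

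In the first four rows completers are unbiased by assumption. In the last two either method can be the worse one.

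**5. Rejection rate, for scale only.** Assume no true T3 change, n3 = 50, a t-test on the changes, and alpha 0.10 as in SAP 5.1, taken as two-sided. With SD of change 2.0 (assumed), simulation with 100,000 replicates gives:

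| T2 gain | 5 fills | 10 fills | 20 fills |
|---|---|---|---|
| 1.0 | 11.6% | 16.0% | 30.7% |
| 0.5 | 10.5% | 11.5% | 15.6% |

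A separate noncentral-t calculation at the same standardised gains (0.5 and 0.25 SD) gives 11.8%, 16.6%, 31.4% and 10.5%, 11.7%, 15.8%. Using T3 alone gives 10%. With a gain of 1.0 and 20 fills, the rate is 44.3% at SD 1.5 and 23.5% at SD 2.5. For Phase 3 with 28 observed and 12 filled, it is about 13-14% at a gain of 0.25 SD and 22-24% at 0.5 SD.

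**The case against.** The rule is prespecified. It is written out just above the label, and 5.2 sends the reader to it, so it does not by itself contradict 4.1.3. That stands, but it does not make a T2 change a T3 change, and nothing in the planned output shows which values were filled.

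The more natural reading of 3.1, under its intent-to-treat heading and alongside protocol 10.4, may be that T3 is required. The effect is then negligible. This is fair, and it is why the numbers above are conditional. But the fallback would then serve almost no purpose, and the text does not choose.

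The contrast with the other 11 variables is partly a matter of data. Self-efficacy is the only one for which the SAPs derive a T2 score. The career-attitude scales are described as measured only at T1 and T3, and the specimen forms are scheduled only then, so at least nine of the 11 had no T2 value to carry. That explains the exception. It does not remove the mixing of time points.

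The 0-2 week interval is nominal. Under protocol 8.2, people attending one to three sessions may do T2 up to 14 weeks (Phase 2) or 6 weeks (Phase 3) after baseline. Protocol 10.4's cases-with-endpoint analysis is also not withdrawn by either SAP. Both points are correct, and the second supports the fix.

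Finally, completers can be more biased than the filled set, as the fifth row of the bias table shows. This stands. The case for change is that the result should be what its label says, not that completers are unbiased.

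**Conclusion.** The concern holds in both SAPs. A stated rule can put end-of-training change into a primary result labelled T3-T1, and 3.1 does not say whether the people affected are analysed. If T3 is required, the effect is negligible. If it is not, the Phase 2 ceiling is 28.6% of values at the planned minimum retention, and the illustrated shift runs from −0.14 to +0.29 points. Those shifts and the rejection rates rest on assumed gains, SD and numbers filled. The documents support only the ceiling. The matter should be settled before analysis, but it does not threaten the feasibility and acceptability objective, and no power calculation rests on it.

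**What to change.** In both SAPs:
- Set `JOBSEEK_T1T3_1` to missing when T3 is missing, and report T2 minus T1 under its own variable name.
- State in 3.1 that the T1-to-T3 change set consists of T3 completers, and define what completing T3 means.
- Make the observed-T3 result the main self-efficacy analysis, as the cases-with-endpoint analysis of protocol 10.4.
- If the T2-filled version is kept, label it as such, flag and count the filled values, and report it only as a sensitivity analysis.
- Where a substantial share is missing, run the multiple imputation that protocol 10.4 already provides for, using T1 and T2, beside the completers result.

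The cost is wording and a few lines of code in each SAP, with no new data. The downside is a smaller main analysis set whose members may differ from those who dropped out. Imputation also relies on a missing-at-random assumption that the observed data cannot test.
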